- Patterns of treatment decisions\actions made after making the clinical assessment of IBD activity (incl. therapeutic de-escalation, escalation, without changes) depending on scenario of achievement /non-achievement of T2T treatment goals.

- Challenges of implementing a T2T strategy in UC and CD in real clinical practice (incl. clinicians related factors, patient related factors, disease related factors).
- Healthcare resources utilization for patients with moderate to severe UC/ CD: hospitalizations due to complications, IBD related surgeries, disability determination (frequency, percentage of UC and CD patients, who used these healthcare resources) within 2 years before enrolment and during 12-months observational period
- Percentage of UC and CD patients with surgical treatment in 2 years history and during 12-months observational period in frames of this study: indications, types of surgeries, complications

Safety outcome:

- Patient incidence and type of adverse drug reactions related to IBD treatment occurring during 12-months treatment period within routine clinical practice by treatment type (biologics or non-biological therapy) and treatment history (biologic treatment naïve or with prior biological treatment);
- Patient incidence and type of serious adverse events related to IBD treatment occurring during 12-months treatment period within routine clinical practice by treatment type (biologics or non-biological therapy) and treatment history (biologic treatment naïve or with prior biological treatment).

Exploratory outcomes:

- Number of moderate to severe UC and CD patients with TB positive tests results/active TB before start of biological therapy.
- Number of moderate to severe UC and CD patients with TB reactivation/occurrence in frames of this study by treatment type (biologics or/and non-biological treatment).

7 Study Administrative Structure

Contact and responsibilities of all parties contributing to the study, including all investigators, are detailed below.

The sponsor is responsible for all study-related activities including study set-up activities and study documentation development. The responsible CRO for specific study-related activities will perform these activities in full or in partnership with the sponsor.

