12.2 Tabulated overview of data collection

The documentation of study data will be reported by investigators via electronic case report form (eCRF).

Assessment / Procedure	Retrospective data collection*	Baseline visit (V1, Day 1)	Observational visit (V2, Month 6)	Final visit (V3, Month12)
Informed consent		X		
Patients' eligibility assessment: Inclusion/exclusion criteria		X		
Date of visit		X	X	X
Demographics data		X		
Disability		X		
Physical examination		X	X	X
Medical history / Concurrent medical conditions	X	X		
History of IBD	X	X		
IBD family history		X		
IBD assessment	X	X	X	X
Disease activity data		X	X	X
IBD status		X	X	X
Laboratory and instrumental evaluation of IBD **	X	X	X	X
IBD treatment	X	X	X	X
Healthcare resources utilization	X	X	X	X
Concomitant treatment		X	X	X
Physician Survey		X		X
Adverse events			X	X

* Retrospective data within two years before of patient enrolment in the study will be collected at Visit 1 after the signing of the informed consent form

**All examinations (laboratory tests and instrumental exams) are done in accordance with clinical routine practice and physician's decision. All examinations results should be registered in electronic CRF only if they are done in routine practice.

12.3 Data collected on the Baseline visit (V1), including collection of Retrospective data within two years before of patient enrolment in the study

The baseline visit takes place at the physician's office. Data to be collected:

- Date of Informed consent form signing (day, month, year);
- Inclusion/exclusion criteria;
- Date of visit (day, month, year);
- Demographics data (gender, date of birth, ethnicity, region of residence, smoking status, employment status (employed, unemployed, retired, student, other));
- Disability:
 - Disability group
 - Cause of disability
 - Year of disability
- Physical examination: height (cm) and weight (kg), body mass index calculation;
- Medical history/Concurrent medical conditions (disease, date of diagnosis, resolution date);
- History of inflammatory bowel disease (IBD):
 - Type of inflammatory bowel disease (ulcerative colitis (UC) or Crohn's disease (CD)),
 - Date of IBD diagnosis,
 - Date of IBD symptoms onset,
 - Availability of observation in the current investigational site within previous 2 years
- IBD family history (degree of relationship);
- Clinical course of IBD (acute, chronic continuous, chronic recurrent);
- IBD assessment for the last 2 years and at the time of the baseline visit:

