12.4 Data collected at the Observational visit (V2) and Final Visit (V3)

Data to be collected directly on Observational visit (V2) and Final visit (V3):

- Date of visit (day, month, year)
- Type of visit: visit to physician office or distant contact
- Physical examination: weight (kg), body mass index calculation;
- IBD assessment at the time of the visit:
 - Disease extent according to the following Montreal Classification categories;
- Disease activity data at the visit will consist of specified signs and symptoms depending on the disease type:
 - CD: abdominal pain severity, number of liquid stools per day, presence of an abdominal mass, endoscopic findings (if done), documented presence of CD complications, and Harvey Bradshaw Index or other documented disease activity scales (if applicable).
 - UC: frequency of stools/day, rectal bleeding, endoscopic findings (if done), physician global assessment of disease severity, and Mayo scores or other documented disease activity scales (if applicable).
- IBD status (with current/last available data by the date of the visit):

- IBD status as judged by investigator (remission, incomplete remission, flare, others), nature of remission at the time of examination;
- IBD flare(s);
- Systemic (extra intestinal) IBD manifestations;
- IBD complications;
- Vaccination in accordance with IBD treatment guidelines.
- Laboratory and instrumental evaluation of IBD (if done within routine practice) - for details please section 12.8;
- IBD treatment;
- IBD surgical treatment;
- Healthcare resources utilization;
- Concomitant treatment
- Adverse events and adverse drug reactions (seriousness, severity, causality, start and stop dates, action, frequency, outcomes):
 - adverse drug reactions on IBD treatments,
 - adverse events on Entivyo® (Vedolizumab) treatment,
 - serious adverse events on IBD treatments (including Entivyo® (Vedolizumab) treatment).

All adverse events and adverse drug reactions must be documented on the Adverse Report Form which is appended to the Case Report Form.

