12.9 Healthcare resources utilization (HCRU)

Resource utilization will be captured from the patients' medical records:

HCRU will be calculated for hospitalizations related to IBD complications, IBD-related surgeries as available in the medical record and captured in the eCRF.

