### 5.3.3 Collection of data on the continuous basis

All data described below should be collected through whole observational prospective 1-year period of patients within the periods: Baseline visit -Visit 2, Visit 2 - Visit3 (independently of actual number of patient's visit to the clinic):

- IBD treatment;
- IBD surgical treatment (indications, types of surgeries, complications, presence of stoma, etc.);
- Results of diagnostic methods used (within the period since last visit);
- Healthcare resources utilization;
- Concomitant treatment;
- Adverse events and adverse drug reactions (seriousness, severity, causality, start and stop dates, action, frequency, outcomes):
  - adverse drug reactions on IBD treatments, ○ adverse events on Entivyo® (Vedolizumab) treatment,
  - serious adverse events on IBD treatments (including Entivyo® (Vedolizumab) treatment).

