#### Secondary endpoints (outcomes):

- Distribution of socio-demographic variables in patients with moderate to severe UC/CD treated with biologics or/and non-biological treatment;
- Distribution of clinical variables in patients with moderate to severe UC/CD treated with biologics or/and non-biological treatment. Clinical characteristics include family history of IBD, smoking habits (no smoker, ex-smoker and current smoker), medical history comorbidities, disease characteristics (age of disease onset, location of disease, clinical course, disease severity, intestinal and systemic (extraintestinal) manifestations, complications in history and during the study observational period, etc.);
- Description of methods used for documentation of disease activity in routine practice (incl. clinical, endoscopic, lab, histological), and frequency of objective CD/UC disease activity assessment using different methods;
- Percentage of moderate to severe IBD patients achieved clinical and combined clinical and endoscopic remission (based on T2T definitions);
- Percentage of patients with moderate to severe IBD with at least one episode of failure of biological therapy or/and non-biological therapy (e.g., dose escalation of biologics, switching to another therapy, IBD-related surgery, medication augmentation);
- Patterns of treatment decisions\actions made after making the clinical assessment of IBD activity (incl. therapeutic de-escalation, escalation, without changes) depending on scenario of achievement /non-achievement of T2T treatment goals;
- Challenges of implementing a T2T strategy in UC and CD in real clinical practice (incl. clinicians related factors, patient related factors, disease related factors);
- Healthcare resources utilization for patients with moderate to severe UC/CD: hospitalizations due to complications, IBD related surgeries, disability determination

Protocol ID	MACS-2017-102279	STATISTICAL ANALYSIS PLAN	Page 16 of 41	
IP	N/A		Date	30.12.2021
ID	MACS-2017-102279_SAP		Version	v1.2 final

(frequency, percentage of UC and CD patients, who used these healthcare resources) within 2 years before enrolment and during 12-months observational period;

- Percentage of UC and CD patients with surgical treatment in 2 years history and during 12-months observational period in frames of this study: indications, types of surgeries, complications.

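### Disability determination is an outcome for the 12-month follow-up, but the data the plan lists after Visit 1 do not include it, and year-only dating blurs the 2-year look-back

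*Protocol*

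**What the plan says.** Protocol 6.2 places disability inside the healthcare-resource secondary outcome, next to hospitalizations and surgery, and gives it two windows: "disability determination (frequency, percentage of UC and CD patients, who used these healthcare resources) within 2 years before enrolment" and, as the sentence continues, the 12 months of observation. SAP 6.1 lists the same outcome with the same windows, "within 2 years before enrolment and during 12-months observational period".

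The collection side reads differently:

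- **Schedules (Protocol 12.2, SAP Table 1).** Disability has its own row, marked at Visit 1 only. Healthcare resource utilization is a separate row, marked for the retrospective period and for Visits 1, 2 and 3.
- **Visit 1 fields (Protocol 12.3, SAP 5.3.1).** Disability group, cause and "Year of disability". Consent and visit dates, by contrast, are specified to the day.
- **Visit 2 and 3 lists (Protocol 12.4, SAP 5.3.2).** Both include resource utilization. Neither names disability.
- **Continuous collection (SAP 5.3.3).** "All data described below should be collected through whole observational prospective 1-year period of patients", followed by treatment, surgery, diagnostics, resource utilization, concomitant treatment and adverse events. Disability is not named.
- **Definition of resource use (Protocol 12.9).** "HCRU will be calculated for hospitalizations related to IBD complications, IBD-related surgeries as available in the medical record and captured in the eCRF".
- **Planned analysis (SAP 8.1.3).** Hospitalizations, surgeries and a percentage of patients using resources. Disability is not named.

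**The concern.** An outcome stated for a follow-up period needs a data item in that period. For disability the only listed item is a baseline one, and the resource-use item that continues through follow-up is defined without it. If sites follow the plan as written, the 12-month part of this outcome has nothing behind it. Protocol 6.2 also wants outcomes split by whether clinical remission was reached during the study, and that split could not be made for new disability.

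Nothing later in the plan repairs this. Protocol 15.2 confines the descriptive analysis to the data listed in section 12, and both Protocol 15.2.5 and SAP 8.4 rule out imputation. The outcome is not incidental to the study: Protocol 5.1 presents disability in young and middle-aged patients as a major burden of IBD.

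The retrospective part has a lesser problem. A 24-month look-back counted from an enrolment date cannot be applied exactly to events known only by calendar year.

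**Working it through.** The documents give no figure for disability, so there is none to reproduce. The sample-size calculation (Protocol 15.4, SAP 8.2) concerns failure of biologic therapy and does not bear on this point.

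**Prospective part: every listed source that could carry it**

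| Possible source | Covers follow-up? | Names disability? |
|---|---|---|
| Disability row and fields (Protocol 12.2, 12.3) | No, Visit 1 only | Yes |
| Visit 2/3 lists (Protocol 12.4, SAP 5.3.2) | Yes | No |
| Continuous list (SAP 5.3.3) | Yes | No |
| Resource use as defined (Protocol 12.9) | Yes | No |
| Resource-use analysis (SAP 8.1.3) | Yes | No |

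No row has yes in both columns. The serious-adverse-event route does not fill the gap. Persistent disability is a seriousness criterion (Protocol 13.1.3), but it classifies adverse events. What is reported is serious events on IBD treatments (Protocol 13.2.3), and insufficient response is not an adverse event (Protocol 13.1.2). A disability group granted because of the disease itself need not appear there.

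**Retrospective part: what a year-only date costs**

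Inputs: a look-back of 2.0 years (Protocol 6.2) and dates known by calendar year (Protocol 12.3). Assumptions, not in the documents: determinations occur at a constant rate, and enrolment is spread evenly over the calendar year. Let a patient enrol a fraction f of the way through year Y.

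- Events in Y-1, and in Y before enrolment, are certainly inside the window. Only Y-2 is ambiguous.
- Counting Y-2, Y-1 and Y covers 2 + f years, so the overcount is (2 + f - 2)/2 = f/2.
- Counting only Y-1 and Y covers 1 + f years, so the undercount is (2 - 1 - f)/2 = (1 - f)/2.

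| f | Overcount with Y-2 | Undercount without Y-2 |
|---|---|---|
| 1/12 | 4.2% | 45.8% |
| 0.25 | 12.5% | 37.5% |
| 0.50 | 25.0% | 25.0% |
| 0.75 | 37.5% | 12.5% |
| 11/12 | 45.8% | 4.2% |

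The mean of f under even enrolment is 0.5, so each rule is off by 25% on average, in opposite directions. As an illustration with an assumed rate of 5% of patients per year, a true 2-year figure of 2 × 5% = 10% would be reported on average as 2.5 × 5% = 12.5% or 1.5 × 5% = 7.5%. At 2% per year, a true 4% becomes 5% or 3%. The documents do not say which counting rule applies.

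The two rules do bracket the truth, because 1 + f ≤ 2 ≤ 2 + f for any f between 0 and 1.

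**The case against.** The best reply is that follow-up data are in fact scheduled. Protocol 6.2 names disability determination as a component of resource utilization, and resource utilization is marked at Visits 2 and 3 and collected continuously. On that reading the Visit 1 Disability row is only a baseline descriptor, and the resource-use page could carry new determinations. SAP 8.1.3 keeps a line for the percentage of patients using resources, which could include them. Neither the eCRF nor the table shells of SAP section 9 are in the text available for review.

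This stands in part. It rules out saying that follow-up disability cannot be measured, or that every new determination is lost. A reader might infer either from the schedule, but both depend on an eCRF that cannot be seen. It does not remove the conflict: Protocol 12.9 defines resource use without disability, and a site or database builder following that definition would not collect it.

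Two other strong readings also fail. A reader might call the retrospective determinations misdated, but the recorded year is coarse rather than wrong, and only Y-2 is affected. A reader might also fear that a blank will be reported as no new disability. Nothing in the documents says an uncollected item becomes zero, and percentages are based on non-missing observations (Protocol 15.2.1, SAP 8.1.1).

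Finally, this is one component of one secondary outcome in a descriptive study. That is fair, and it limits the weight of the point.

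**Conclusion.** The point holds as an inconsistency between the stated outcome and the listed data. Protocol 6.2 and SAP 6.1 promise disability determination over 12 months of follow-up, and on the plan as written 0 of those 12 months has a listed disability item. The conclusion is limited to the data the plan lists, and an eCRF page that captured disability would answer it.

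The look-back limitation is secondary. Under a constant event rate and even enrolment, the 2-year figure is off by about 25% on average, upward or downward depending on how Y-2 is treated, with a range of about 4% to 46% across enrolment months. A related gap is that a single group, cause and year entry does not say whether it is a first or a repeat determination, which leaves the frequency part of the outcome undefined.

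No primary outcome or sample-size figure is affected. The change should be made, but it does not threaten the study.

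**What to change.** First check whether the eCRF captured disability at Visits 2 and 3. If it did, state the source and bring Protocol 12.9 and SAP 8.1.3 into line with the outcome.

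If data can still be collected:

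- Add disability determination (group, cause, month and year) to the resource-use definition in Protocol 12.9, to the Visit 2/3 lists and SAP 5.3.3, and to the analysis in SAP 8.1.3.
- Record month and year at Visit 1 as well.
- Say whether first or repeat determinations are counted.

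Data collection was planned to end in Q3–Q4 2021 (Protocol 10.2) and the current SAP is dated 30.12.2021, so that route may be closed. If it is closed and the eCRF did not capture the item:

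- Retrieve dated determinations from medical records, or remove disability determination from the 12-month outcome and state that it was not collected, not that it was zero.
- Report status at Visit 1, and give the 2-year figure as bounds: the lower counting Y-1 to enrolment, the upper counting Y-2 to enrolment. Reporting Visit 1 status alone would discard determinations that can be placed in the window.

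The cost is one extra eCRF field group filled from records, with no patient procedure, or record retrieval, or a narrower secondary outcome.

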6.1 Study objectives

The purpose of this study is to collect information regarding the real life practice of moderate to severe inflammatory bowel disease (IBD) management in Russia, Belarus and Kazakhstan: to document treatment patterns, treatment outcomes in patients with IBD particularly on the use of available biologic therapies.

Primary objective:

- To characterize the treatment patterns associated with biologics agents use or non-biological therapy (i.e. 5-ASA, immunosuppressive agents (including azathioprine (AZA), 6-mercaptopurine (6-MP), methotrexate (MTX), cyclosporine A), corticosteroids) in patients with moderate to severe Ulcerative Colitis (UC) and moderate to severe Crohn's Disease (CD).

Secondary objectives:

- To characterize patients treated with biologics or/and non-biological treatment (i.e. 5-ASA, immunosuppressive agents (including azathioprine (AZA), 6-mercaptopurine (6-MP), methotrexate (MTX), cyclosporine A), corticosteroids) in terms of demographics, medical, and treatment histories;
- To evaluate and describe the implementation and achievement of Treat-to-target (T2T) goals in real-world clinical practice in moderate to severe IBD patients treated by biological and non-biological therapy during 2 years before enrolment and 1 year observational period after enrolment by treatment type 1) to assess the extent to which proposed Treat to Target goals are achieved in moderate to severe UC/CD patients 2) to describe how and when UC/CD disease activity is assessed 3) to evaluate the potential challenges to achieving T2T targets during routine care ;
- Establish the impact on healthcare resources utilization for patients with moderate to severe UC and CD

Safety Objective:

- To describe the incidence of real-world safety data occurred during 12-months treatment period within routine clinical practice by treatment type (biologics or non-biological IBD therapy) and treatment history (biologic treatment naïve or with prior biological treatment).

Exploratory objective:

- To assess TB in moderate to severe IBD patients receiving biologics and/or non-biological treatment.

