11.1 Inclusion Criteria

Every eligible patient at participating investigational sites must meet the following criteria:

Inclusion criteria:

1. Male and female patients 18 years or older by the time of enrolment
2. Confirmed diagnosis of Crohn's disease or ulcerative colitis for at least 2 years prior to enrolment in the study.
3. The presence of a moderate to severe IBD flare at the time of enrolment or in patient anamnesis within 2 years before enrollment treated with steroids or/ and immunosuppressive agents or/ and biologic therapy. IBD flare(s) must be confirmed in the source documentation.
4. Current treatment with steroids or/ and immunosuppressive agents or/ and 5-ASA or/ and biologic therapy
5. Written informed consent, signed before the participation in the study begins.

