 - Disease extent according to the following Montreal Classification categories;
 - Systemic (extra intestinal) IBD manifestations;
 - IBD complications;
 - Vaccination in accordance with IBD treatment guidelines.
- Disease activity data at baseline visit will consist of specified signs and symptoms depending on the disease type:
 - CD: abdominal pain severity, number of liquid stools per day, presence of an abdominal mass, endoscopic findings (if done), documented presence of CD

complications, and Harvey Bradshaw Index or other documented disease activity scales (if applicable).

- UC: frequency of stools/day, rectal bleeding, endoscopic findings (if done), physician global assessment of disease severity, and Mayo scores or other documented disease activity scales (if applicable).
- IBD status at baseline visit:
 - IBD status as judged by investigator (remission, incomplete remission, flare, others), nature of remission at the time of examination;
 - IBD flare(s);
- Laboratory and instrumental evaluation of IBD for the last 2 years and at the time of the baseline visit (if done within routine practice) - for details please section 12.8;
- IBD treatment:
 - IBD treatment for the last 2 years and at the time of the baseline visit;
 - IBD surgical treatment for the last 2 years and at the time of the baseline visit;
- Healthcare resources utilization for the last 2 years and at the time of the baseline visit;
- Concomitant treatment.

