#### 8.1.3 Assessment of secondary and exploratory endpoints

**Each original treatment combination** (defined as the treatment combination that was used by the patient at the very start of retrospective observation period, i.e. first recorded treatment combination in the study) will be tabulated by the below listed parameters using the generic table format below (see example tables: Table 10, Table 11, Table 12 and Table 6):

- Demographic data;
- Disease activity at Visits 1, 2, 3 (Mayo, Harvey-Bradshaw indices);
- Disease status assessed by investigator at Visits 1, 2, 3;
- Frequency (percentage) of clinical, endoscopic and histologic remission at Visits 1, 2, 3 and retrospective period of observation;
- Extent of lesion at Visits 1, 2, 3;
- Systemic (extraintestinal) manifestations at Visits 1, 2, 3;
- Total number, duration and severity of disease exacerbations by Visit 1, 2 and 3;
- Total number, type and duration of disease complications by Visit 1, 2 and 3;
- Laboratory and instrumental assessments at Visits 1, 2, 3;
- Percentage of patient with surgical treatment by Visits 1, 2, 3 grouped by:
  - Indication;
  - Surgery type;
  - Presence of complications.
- Number of surgeries by Visits 1, 2, 3;

Protocol ID	MACS-2017-102279	STATISTICAL ANALYSIS PLAN	Page 25 of 41	
IP	N/A		Date	30.12.2021
ID	MACS-2017-102279_SAP		Version	v1.2 final

- Percentage of patients with at least one episode of failure or biological or/and non-biological therapy (e.g., dose escalation of biologics, switching to another therapy, IBD-related surgery, medication augmentation) by Visits 1, 2 and 3;
- Separately for patients who achieved / not achieved T2T treatment goals (based on the clinical assessment of IBD) by Visits 1, 2 and 3:
  - Presence of therapeutic de-escalation;
  - Presence of therapeutic escalation;
  - Continuation of therapy without any changes.
- Healthcare resources utilization:
  - Hospitalizations due to complications;
  - IBD-related surgeries;
  - Percentage of patients that used healthcare resources;
- Only for biological therapy - percentage (by Visits 1, 2, 3) of patients with:
  - Positive test results for TB before the start of biological therapy;
  - Active TB before the start of biological therapy;
- Percentage of patients by Visits 1, 2, 3 with:
  - Reactivation of TB;
  - New occurrence of TB.

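### Hospitalisation and surgery percentages cover 24 months before and 12 months after enrolment with no common time base, so the two figures for the same outcome are not comparable

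*Protocol*

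**What the plan says.** Protocol 6.2 has a secondary outcome on healthcare use, covering admissions for complications, IBD surgery and disability determination. It is to be given as the frequency and percentage of patients with either disease "who used these healthcare resources) within 2 years before enrolment and during 12-months observational period". A second outcome is the "Percentage of UC and CD patients with surgical treatment in 2 years history and during 12-months observational period", with indications, types and complications. The related objective in Protocol 6.1 is to "Establish the impact on healthcare resources utilization for patients with moderate to severe UC and CD". It names no comparator.

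Two entry criteria in Protocol 11.1 shape the earlier window. Criterion 2 asks for "Confirmed diagnosis of Crohn's disease or ulcerative colitis for at least 2 years prior to enrolment in the study", so every patient has 24 months of diagnosed disease before entry. Criterion 3 asks for "The presence of a moderate to severe IBD flare at the time of enrolment or in patient anamnesis within 2 years before enrollment"; the flare must have been treated and be documented at source. Nothing comparable conditions the follow-up year.

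SAP 8.1.3 lists admissions, surgeries and "Percentage of patients that used healthcare resources", without a window or a person-time denominator. It also lists the percentage of patients operated on and the number of surgeries for Visits 1, 2 and 3, without saying whether these are cumulative or per interval. The same section uses six-month blocks over the look-back for treatment patterns, but not for these outcomes. Protocol 12.3 records "Healthcare resources utilization for the last 2 years and at the time of the baseline visit" as one item. The bias discussion in Protocol 15.2.4 mentions neither the unequal windows nor flare-based entry.

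**The concern.** The percentage of patients with at least one event rises with the length of the window, so a 24-month figure and a 12-month figure differ even when nothing has changed. Entry through a recent flare adds a second distortion. Protocol 4.2 describes alternating active disease and remission, and flares plausibly drive admission and surgery, so a look-back chosen to contain a flare will tend to show more use than an unselected year.

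Both windows appear in the same outcome definition, under an objective about impact with no stated contrast, and no caution is given. A reader who sets the two percentages side by side could take an unchanged burden for an improvement during the study year.

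**Working it through.** The documents give no admission, surgery or flare rate, so there is no planned figure to reproduce. All rates below are assumptions, shown over a range. Every scenario assumes no true change in disease or care. The ratio is the later percentage divided by the earlier one.

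**Step 1: window length alone.** With a constant rate and 12-month risk P12, P24 = 1 − (1 − P12)², so the ratio is 1/(2 − P12). For heterogeneity between patients, a gamma frailty with variance v gives L = ((1 − P12)^(−v) − 1)/v and P24 = 1 − (1 + 2vL)^(−1/v).

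| P12 | P24, no frailty | Ratio | Ratio, v = 1 | Ratio, v = 3 |
|---|---|---|---|---|
| 5% | 9.8% | 0.51 | 0.53 | 0.55 |
| 10% | 19% | 0.53 | 0.55 | 0.59 |
| 20% | 36% | 0.56 | 0.60 | 0.67 |
| 30% | 51% | 0.59 | 0.65 | 0.74 |
| 50% | 75% | 0.67 | 0.75 | 0.84 |

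The direction does not depend on the assumed rate.

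**Step 2: add selection on an earlier flare.** Let flares be Poisson at μ per year, each leading to use with probability q, and condition on at least one flare in the 24 months. Then P24 = (1 − exp(−2μq))/(1 − exp(−2μ)) and P12 = 1 − exp(−μq). With q = 0.3:

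| μ per year | Before | After | Ratio |
|---|---|---|---|
| 0.3 | 36.5% | 8.6% | 0.24 |
| 0.5 | 41.0% | 13.9% | 0.34 |
| 1.0 | 52.2% | 25.9% | 0.50 |

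Over q = 0.1 to 0.5 the ratio runs from 0.23 to 0.54. With frailty variance 1 to 2 and q = 0.3 it is 0.32 to 0.57.

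**Step 3: allow entry in flare.** Criterion 3 also admits a flare at enrolment. Let a share f enter that way with no condition on their earlier window, the rest as in step 2, with q = 0.3 and μ from 0.3 to 1.0.

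| f | Ratio if the entry episode is counted after enrolment | Ratio if counted in the look-back |
|---|---|---|
| 25% | 0.49 to 0.62 | 0.23 to 0.48 |
| 50% | 0.76 to 0.84 | 0.22 to 0.46 |
| 75% | 0.91 to 1.36 | 0.21 to 0.44 |

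For example, at f = 75% and μ = 0.3 the figures are 21.5% before and 29.2% after if counted after enrolment, but 40.3% and 8.6% if counted in the look-back.

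**Step 4: what annualising repairs.** For events per patient-year, the window-length ratio becomes 1.00. The ratio under the step 2 selection is 1 − exp(−2μ): 0.45, 0.63 and 0.86 at μ = 0.3, 0.5 and 1.0, or 0.61 to 0.91 with frailty variance 1 to 2. Rates therefore remove the length artefact but not the selection.

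**Step 5: early leavers.** Taking the 10% drop-out from Protocol 15.4, lost on average at six months, a 12-month risk of 20% becomes 0.9 × 0.20 + 0.1 × (1 − 0.8^0.5) = 19.1%. This is a small further fall.

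**The case against.** The strongest reply is that no before-after comparison is planned. Protocol 15.2.2 calls the analysis descriptive and tabulates retrospective data separately. The only gloss on impact, in the rationale (Protocol 5.2), concerns sub-optimal therapy. The planned splits by disease, therapy type and remission status can be read within one window, where length does no harm. All of this stands, and it limits the point to comparability and labelling. It does not supply the missing contrast or warn the reader.

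The outcome also includes a frequency, and SAP 8.1.3 includes a number of surgeries. If these are event counts, a yearly figure could be derived, but neither document says so. If the SAP's visit-based figures are cumulative, they cannot fall from visit to visit; if they are per interval, a 24-month look-back sits beside two intervals of about six months.

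A reader might infer that a large fall after enrolment is built in. The documents do not support that. Entry in flare is allowed, and step 3 shows that the fall can shrink or reverse. Recording baseline-visit use together with the look-back points towards a fall, but the cut-off is not stated. Incomplete look-back records would lower the earlier figure and also work against a fall.

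Finally, the study describes patients who meet its flare criterion, so the earlier figure is not wrong for that population. It is only a poor reference for the year that follows.

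**Conclusion.** The point holds as a reporting weakness in two descriptive secondary outcomes. As defined, the before and after percentages for admissions and surgery are not comparable. Length alone puts the later figure at 0.51 to 0.67 of the earlier one for assumed 12-month risks of 5% to 50%, so an unchanged burden looks like a fall of about a third to a half. Strong heterogeneity (frailty variance 3) moves this to 0.55 to 0.84. The length effect is certain in direction. The flare-selection effect is probable, but its size and even its sign depend on how many patients enter in flare and where that episode is counted.

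It does not follow that the study intends to read impact from this difference; the documents specify no such analysis. Nor does the argument extend to disability determination, which the visit table in Protocol 12.2 collects at baseline only.

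**What to change.** In Protocol 6.2 and SAP 8.1.3:

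- Report admissions and surgeries as events per patient-year with 95% CI, using observed time for early leavers.
- Where event dates allow, add percentages per 12-month block: −24 to −12, −12 to 0 and 0 to 12 months.
- State on which side of the cut-off use at the baseline visit is counted, and whether the figures for Visits 1, 2 and 3 are cumulative or per interval.
- Show results separately for patients in flare and not in flare at Visit 1.
- State that annualising removes the window-length artefact but not the selection on flare, so the before-after difference is not an estimate of impact.

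The cost is SAP wording and one extra set of tables. IBD status at Visit 1, visit dates and date of last contact are already collected (Protocol 12.3 to 12.5). If event dates are missing, whole-window rates can still be formed from event counts. The downside is that before-after statements become weaker.
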